### **Health-related quality of life (HRQOL)**

Since assessment of clinical outcomes (OIs, immune status CD4, survival rate) might not be reflect non-medical aspects of PLHIV, such as interpersonal, mental health and social functions, health-related quality of life will be used to measure the change in theses dimensions among participants. In this study, we employ EQ5D-5L (The EuroQoL-5 Dimensions-5 Levels) for measuring health-related quality of life of patients. This measurement provides a health profile and a single index value for health status, which includes five dimensions: Mobility, Self-care, Usual activities, Pain/Discomfort and Anxiety/Depression. EQ5D has been used among PLHIV in Vietnam, and shown to be valid for measuring HRQOL for PLHIV[22]. Moreover, EQ5D also provides a health utility score that is very useful for evaluating cost-effectiveness of the intervention. EQ5D will be assessed at the time of enrollment and every 6months (at 6- and 12-month follow-ups) upon patient's choice. The HRQOL Form will be filled after follow-up form

(see Appendix). For patients who enrolled before HRQOL questionnaire was used, the EQ5D will be assessed only at 6- and 12-month follow-ups.

## **8. Study Implementation**

### **8.1. Crag screening program launch meeting**

A meeting will be held to launch the screening project and to discuss implementation. The meeting will be attended by investigators, representatives from all sites, representatives from Centers for Disease Control and Prevention (CDC), other United States government agencies, other donors and implementing partners and will be chaired by VAAC.

### **8.2 Pre-study training**

A training course is mandatory for the study implementation. It will be conducted before study implementation begins and after the launch meeting has been done. During implementation of the study, refresher training will be conducted in order to maintain competencies in the study protocol and address gaps in care and difficulties that arise in implementation.

#### **Clinician and laboratory staff training**

1. Before training, each participating OPC, laboratory, and hospital will be asked to select a POC person who will be in charge of coordinating the cryptococcal screening program at their site. Although others at each site may additionally be involved in training, the POC will be responsible for communication between their site and the other sites (OPC, lab, and hospital), and ensuring that data are collected appropriately and in a timely fashion. Additionally, a back-up POC will be identified at each site, in the event that the POC is away, leaves the facility, or cannot fulfill their duties.
2. Training for both clinicians and laboratory staff will be carried out in parallel in Hanoi and Ho Chi Minh City by the investigators and subject matter experts from CDC-Vietnam, CDC-Atlanta, and NHTD. Initial trainings will take place prior to the implementation of the cryptococcal screening program with planned refresher trainings as needed to account for personnel turnover and quality assurance.
3. Clinician training will include outpatient-site training at the participating OPCs, and

## Cryptococcal Retention In Care Study (CRICS)

inpatient-site training among referral hospital. Training will be conducted for each OPC and any relevant hospital staff. The following topics will be covered:

- a. Basic information about cryptococcal disease, including early and disseminated infection
- b. Explanation of the rationale behind the implementation of this screening program
- c. Review of the algorithm for implementation
- d. Role-playing using different clinical scenarios in order to ensure proper adherence to the algorithm and flow of patients.
- e. Good clinical practice

4. Laboratory training will be inclusive of both outpatient participating laboratory staff serving the OPCs participating in the implementation of this screening program, and in-hospital laboratory staff who will be performing CrAg LFA testing on CSF specimens at Tropical Diseases Hospital and National Hospital for Tropical Diseases. Training for laboratory staff will include:
  - a. Instructions and practice in performing and interpreting the LFA CrAg test
  - b. Review of the protocol for communicating CSF CrAg results to OPCs
  - c. Reviewing the standard operating procedures (SOP) portions relevant to the laboratory staff.

Training of all laboratory and clinical staff at all OPCs and laboratories will occur in a two-week period preceding the program roll-out; in-country staff from NHTD, TDH, and CDC will return to the node laboratories, OPCs, and hospitals to provide refresher training as needed. The refresher training and training for new study staff will be performed on site as needed.

### **8.3. Additional training in Phase 2**

Training for relevant staff from network laboratories, non-CRICS sites and affiliated inpatient wards will be conducted by the investigators and experts from CDC-Vietnam, CDC-Atlanta, NHTD and TDH, and other local experts as relevant. The training contents will cover:

- Screening procedures, roles and responsibility of each party in Phase 2
- How to communicate CrAg results with OPCs and handle CrAg-positive results
- Data collection

## Cryptococcal Retention In Care Study (CRICS)

- Reporting requirements regarding the number of screened patients and CrAg+, as well as the any factors that affects the stability of CD4 testing (e.g. the availability of reagents, the functioning of CD4 count machines and any changes to the list of sites that the lab is conducting CD4 testing for) on a regular basis.

### **8.4 Monitoring visits**

#### a. Phase 1

Every 1-2months, the study coordinators/research associates/research assistant/data manager or other study staff will visit each of all study sites to supervise the study and collect data. Every six months, the regular visit will also includePrincipal Investigators or lead-coordinators and refresher training will be included as needed. The monitoring tasks include:

- Checking that patients with  $CD4 \leq 100$  cells/ $\mu L$  have all been screened for CrAg
- Checking the number of newly-enrolled patients
- Checking if all patients enrolled since the last clinical research associate (CRA) visit have signed the informed consent forms.
- Checking that fluconazole dosage of CrAg-positive patients is being changed according to protocol (section 7.4)
- Checking that all CRFs are properly filled.
- Checking the number of newly enrolled patients.
- Recording all emerging issues during implementation, including ascertainment of changes to routine CD4 or viral load testing due to financing or other reasons.

b. Phase 2 labs will be the focal point of contact in Phase 2 as all study activity related to CrAg screening and data collection will take place at labs. Thus, lab monitoring visits will be conducted on a monthly basis. The purpose of such monitoring visits is to:

- The number of CD4 tests performed and number of tests having CD4 count  $\leq 100$  cells/ $\mu L$
- The number of patients tested for CrAg and those with positive CrAg results
- Obtain an updated lists of OPCs and sites that are served by the lab
- The availability of reagents, the functioning of CD4 testing machines, and any factors that might influence the lab's ability to perform CD4 testing

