## 2. Study Objectives and Outcome Measures

**Table 1. Study objectives and outcome measures**

Primary objectives	Outcome measures
1. To estimate the proportion of people living with HIV (PLHIV) who have advanced disease ( $CD4 \leq 100 \text{ cells}/\mu\text{L}$ ) at presentation to HIV care	
 
Proportion of HIV-infected adults who have <math>CD4 \leq 100 \text{ cells}/\mu\text{L}</math>
 

2. To determine the prevalence of CrAg-positivity among HIV-infected patients with $CD4 \leq 100 \text{ cells}/\mu\text{L}$	
 
Proportion of patients who are CrAg-positive among all HIV-infected adults who have <math>CD4 \leq 100 \text{ cells}/\mu\text{L}</math>
 

3. To determine clinical outcomes including common causes of mortality for PLHIV with $CD4 \leq 100 \text{ cells}/\mu\text{L}$ who are enrolled in a programmatic rollout of screening for CrAg	
 
Reported causes of death
 
Proportion of patients with HIV-related hospitalizations at 6 and 12 months
 
Proportion of patients with new AIDS-defining OIs/conditions at 6 and 12 months
 

4. To estimate the 12-month mortality among two groups of HIV-infected patients with $CD4 \leq 100 \text{ cells}/\mu\text{L}$ who are enrolled in care and treatment: 
 
Those who are CrAg-positive and are treated with high-dose fluconazole;
 
Those who are CrAg-negative.
 
	
 
Twelve (12) month all-causes and CM-related mortality among patients who screen CrAg-positive and CrAg-negative
 

Secondary objectives	Outcome measures

5. To estimate the 12-month retention in care among two groups of HIV-infected patients with <math>CD4 \leq 100</math> cells/<math>\mu</math>L who are newly enrolled in care and treatment:
 
 
• Those who are CrAg-positive and are treated with high-dose fluconazole
 
• Those who are CrAg-negative
 
	
 
• Twelve (12) month retention among patients who screen CrAg-positive and CrAg-negative
 

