## 6. Sample size calculation:

The two primary outcomes of the study are 1) the estimate of the percentage of prescreened patients who have  $CD4 \leq 100$  cells/ $\mu L$  and 2) Of those with  $CD4 \leq 100$  cells/ $\mu L$ , the estimate of the percentage who are CrAg+. For these primary outcomes, data will come from both Phase 1 and Phase 2. From study initiation to October 31 2016 (approximately 13 months), we prescreened 2,612 participants, and 1068 of these had a  $CD4 \leq 100$  cells/ $\mu L$ . Of those, 957 enrolled, and 25(2.6%) were CrAg+. Assuming a similar enrollment rate (74 per month), upon the completion of Phase 1 (March 2017), we will have prescreened 3,014 participants and would expect 1,232 to have  $CD4 \leq 100$  cells/ $\mu L$  and 1,104 to be enrolled in the follow up study. Of these, we would expect approximately 29 to be CrAg+.

For Phase 2 (presumably from February 2017 to September 2017), plan to prescreen an additional 1,808 patients. Taking both data from Phase 1 and Phase 2 into account, we would expect to prescreen 4,822 patients and to document 1,972 patients with  $CD4 \leq 100$  cells/ $\mu L$ . In total, we would expect approximately 46 patients to be CrAg+.

Table 3 presents confidence limits for the two primary outcomes based on these assumptions and incorporating a design effect (DEFF) to account for the within-facility clustering of observations. The design effect is computed as  $[1+(m-1) \text{ ICC}]$  where  $m$  is the average number of patients per facility and ICC is the intraclass correlation coefficient. There is no local data on which to base assumptions about the magnitude of the within-clinic correlation in Vietnam, but a recent publication reports intraclass correlation coefficients (ICCs) of about .02 or smaller for health-related variables in an HIV-positive clinic population in sub-Saharan Africa [4]. Taking data from Phase 1 into account only, for the first primary outcome,  $m$  is 137 (3014/22) and for the second primary outcome,  $m$  is 56 (1,232/22). Taking data from both Phase 1 and Phase 2 into account,  $m$  is 219 (4822/22) and is 90 (1972/22) for the first and the second primary outcomes respectively.

**Table 3. Precision for primary study outcomes based on projected enrollment in Phase 1 (through March 2017) and Phase 1 + Phase 2 (projected through September 2017)**

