## **7.2. Subject ID assignment (Phase 1)**

The assignment of participant ID will be only applied in the study sites. Each patient enrolled in the evaluation will be given a subject ID. This subject ID will be independent of the patient's OPC ID, which is assigned to each individual when they are registered at the OPC. The subject ID will take the following format :<XX>-<YYY>

- XX: the letter code(s) assigned to each participating site using alphabetical letters.
- YYY: the number which is assigned to an individual patient. This part has three characters from 001 to 999.

Sequentially numbered subject IDs for each site will be printed and, after consent, assigned to each enrolled participant. A sticker with a pre-printed subject ID will be placed at the top of the first page of all case report forms (CRFs). Accurate records of assigned numbers will be kept and updated into Enrollment log at OPCs (see Appendix 14B: Enrollment Log for OPC) to ensure that no two patients are assigned the same subject ID. The study staff will be responsible for securing the patient's information and minimize the risk of re-identification of the subject.

In Phase 2, screened patients will be given a unique ID which is made of patient's name in abbreviation, age, and OPC code. This would allow the study team to identify patients with duplication of CrAg results and track patients with positive CrAg results for their uptake of fluconazole.

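### Primary outcome 1 is a proportion of patients at presentation to care, but Phase 2 counts it in CD4 tests without indication or an ID above 100 cells/µL, so the pooled figure can be biased, probably but not necessarily downward

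*Protocol*

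**What the plan says.** - **Unit of the outcome.** Table 1 of the Protocol measures objective 1 as "Proportion of HIV-infected adults who have" CD4 ≤100, and the objective places this at presentation to HIV care. Section 6 restates it as "the estimate of the percentage of prescreened patients who have" CD4 ≤100.
- **Source.** Section 6: "For these primary outcomes, data will come from both Phase 1 and Phase 2". For Phase 2 the team will "plan to prescreen an additional 1,808 patients". In total, "we would expect to prescreen 4,822 patients and to document 1,972 patients with" CD4 ≤100.
- **Phase 2 collection.** Section 7.1.2 says physicians do not prescreen in Phase 2. The monthly laboratory visits in section 8.4 collect "The number of CD4 tests performed and number of tests having CD4 count" ≤100. The next item in that list counts patients, but only those tested for CrAg.
- **Identifier.** Section 7.2 gives the Phase 2 ID to screened patients. Its purposes are tracking fluconazole uptake and the following: "This would allow the study team to identify patients with duplication of CrAg results".
- **Indication.** The Phase 2 requisition form has a checkbox separating new enrollment, routine monitoring and presumed treatment failure (7.1.2). Sections 7.3b and 7.4b and the Phase 2 overview in section 10 list CD4 indication as a data item in the context of patients screened for CrAg. The Phase 2 list in 10.1 is general. Section 7.1.2 itself has laboratories record the indication for the CrAg test.

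**The concern.** The outcome needs one record per newly presenting patient. The Phase 2 counts are of tests, and repeat tests are to be expected in the laboratories that supply them:

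- Table 4 schedules CD4 at 6 and 12 months for Phase 1 enrollees. Their follow-up runs on during Phase 2 (Protocol Summary), and section 3 keeps the same laboratories serving the same clinics.
- Phase 2 also admits treatment-experienced patients (section 3), whose CD4 tests are not at presentation.

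A Phase 1 enrollee already in the Phase 1 numerator who is retested on ART and is now above 100 would add only to the Phase 2 denominator. No section provides an ID or a duplicate rule for a patient above 100, and none limits outcome 1 to new-enrollment tests. At stake is a primary outcome with over a third of its planned denominator coming from Phase 2. An error in the counting unit is not covered by the confidence interval.

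**Working it through.** **Inputs (section 6 and Table 3).** Observed to 31 October 2016: "we prescreened 2,612 participants, and 1068 of these had a" CD4 ≤100, so 1,068/2,612 = 40.9%. Planned: Phase 1 1,232/3,014; pooled 1,972/4,822; 22 facilities; ICC 0.02.

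**Reproducing Table 3.** DEFF = 1 + (m − 1) × 0.02; limits = p ± 1.96 × √(p(1 − p) × DEFF / n), with p = 0.409.
- Phase 1: m = 137, DEFF = 3.72, limits 37.5 to 44.3.
- Pooled: m = 219, DEFF = 5.36, SE = √(5.36 × 0.409 × 0.591 / 4,822) = 0.0164, limits 37.7 to 44.1.

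Both match. The calculation treats all 4,822 as distinct patients.

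**Implied Phase 2 part.** Numerator 1,972 − 1,232 = 740. Denominator 4,822 − 3,014 = 1,808. Proportion 740/1,808 = 40.9%. Expected above 100: 1,808 − 740 = 1,068 (by coincidence, the same number as the Phase 1 patients at or below 100 seen to October 2016). Phase 2 share: 1,808/4,822 = 37.5%.

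The 1,808 appears to carry the Phase 1 patient rate forward: 2,612/13 ≈ 201 per month, and nine months at that rate gives 1,808. It makes no allowance for repeat tests.

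**Scenario A: tests at or below 100 reduced to patients, repeats above 100 kept.** Assumption: repeats equal a fraction f of the 1,068. Pooled = 1,972 / (4,822 + 1,068f).

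| f | extra tests | pooled | fall in SEs (1.64 points) |
|---|---|---|---|
| 0 | 0 | 40.9% | 0 |
| 0.1 | 107 | 40.0% | 0.5 |
| 0.2 | 214 | 39.2% | 1.1 |
| 0.5 | 534 | 36.8% | 2.5 |

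The pooled figure reaches the lower limit of 37.7% at 1,972/0.377 − 4,822 ≈ 409 extra tests. That is 38% of the 1,068, or one test above 100 from 37% of the 1,104 expected Phase 1 enrollees (409/1,104).

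**Scenario B: both counts left as tests, as section 8.4 words them.** Repeat fractions a (at or below 100) and b (above 100). Pooled = (1,232 + 740(1 + a)) / (3,014 + 740(1 + a) + 1,068(1 + b)).

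| a | b | pooled |
|---|---|---|
| 0.2 | 0.2 | 40.9% |
| 0.2 | 0.1 | 41.8% |
| 0.3 | 0.1 | 42.6% |
| 0.2 | 0.5 | 38.5% |

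**Scenario C: one new-enrollment CD4 per patient.** 1,972/4,822 = 40.9%, the planned figure.

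The Protocol gives none of f, a or b. The tables show sensitivity and do not predict a result.

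**The case against.** A reader might infer that the numerator is in patients and the denominator in tests, so that the estimate must be biased downward. The text does not support this. Section 8.4 counts both sides in tests, and the ID in 7.2 is not assigned to de-duplicating outcome 1. Scenario B shows that equal repeat rates cancel and that more repeats at low CD4 push the figure up.

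The other side has three further arguments:

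- **The checkbox.** The outcome is defined at presentation, and section 13.2 speaks of monitoring baseline CD4, so restricting to new-enrollment tests would be natural and would remove most repeats. This stands as a possible remedy. It does not close the gap, because no section commits outcome 1 to that restriction, the 8.4 counts are not split by indication, and most mentions of CD4 indication as a data item concern patients screened for CrAg.
- **Section 8.4 is a monitoring list, and the analysis rule may sit in the SAP.** This is partly fair. But it is the only place that sets a Phase 2 count for outcome 1, and an analysis plan cannot turn test totals into patients afterwards. The identifying fields must be captured at the laboratory.
- **Repeats may be few.** Section 3 gives Phase 2 up to 3–6 months (the Summary says at least 6), and CD4 testing is being scaled down. This limits repeats within Phase 2. It does not exclude retests of Phase 1 enrollees whose 6- or 12-month CD4 falls in that window.

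**Conclusion.** The defect holds as a mismatch of unit: patients at presentation in the outcome, CD4 tests of any indication in the Phase 2 counts, and no stated means of linking tests above 100 to patients. The pooled proportion can be biased as a result. Downward is the likelier direction, because retested Phase 1 enrollees and monitored patients on ART would be expected to fall more often above 100. That is a judgement about the patient mix, and the Protocol does not fix the direction.

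The size is unknown. Under Scenario A it runs from about half a standard error (f = 0.1) to beyond Table 3's lower limit (f = 0.5). It is zero if repeat rates are equal on both sides, or if only one new-enrollment test per patient is used. The scenarios assume a true 40.9% in both phases and 1,808 distinct Phase 2 patients.

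**What to change.** - In 7.1.2, 7.2 and 8.4, have laboratories record the coded Phase 2 ID and the CD4 indication for every CD4 test from participating OPCs, not only those screened for CrAg.
- Define the Phase 2 contribution to outcome 1 as one new-enrollment CD4 per patient not already counted in Phase 1, applied to both numerator and denominator.
- Where a laboratory can supply only test totals, leave its Phase 2 counts out of outcome 1 and report them descriptively as tests.

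**Cost.** Two more fields per CD4 log line. The ID is built partly from the patient's abbreviated name, so its wider use should be checked against the consent waiver in 13.2, which refers to aggregate, de-identified data. Some Phase 2 data may be lost to outcome 1, with little loss of precision: Table 3 gives 37.5 to 44.3 for Phase 1 alone against 37.7 to 44.1 pooled, a width of 6.8 against 6.4 points.

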## Cryptococcal Retention In Care Study (CRICS)

- Working closely with lab staff to ensure regular updating the expansion progress and timely data collection.

### **8.5Management Meetings**

A meeting of the study management team will be held annually after implementation of the program. The meeting will involve the PIs and site investigators. Other meetings will include:

- A quarterly teleconference with all investigators
- A monthly meeting with the study investigators in Vietnam

The topics will include:

- Reporting the progress of implementation.
- Reporting emerging issues during implementation.
- Proposing solutions and recommendations for the remaining period.

[figure not shown]
## **9. Specimen collection and processing**

### **9.1. Sample collection**

- Blood specimens will be collected from all patients at the time that routine CD4 count testing is being done. As mentioned above under visit 0, patients who have already had CD4 tests done in the 2 weeks before the enrolment date, the remnant plasma from other routine tests ordered on the day of enrollment will be used for CrAg screening. If no other tests requested on the day of enrollment patients will be asked to provide a fresh sample of blood for CrAg screening.
- CSF specimens will only be collected in patients with suspected meningitis on the basis of symptoms and who consent to LP.
- Urine samples for pregnancy tests will be taken from CrAg+ women who are within the reproductive age group (under 55 years) at the enrollment visit and at follow-up visits for those whose last normal menstrual period began > 5 weeks prior.
- Collection, transportation and storage of specimens will follow national CD4 testing guideline.

## 9.2. CD4 and CrAg LFA testing

The CrAg LFA is a dipstick sandwich immunochromatographic assay. Specimens and specimen diluent are added into an appropriate reservoir, such as a test tube, and the lateral flow device is placed into the reservoir. The test uses specimen wicking to capture gold-conjugated, anti-CrAg monoclonal antibodies and gold-conjugated control antibodies deposited on the test membrane. If CrAg is present in the specimen, then it binds to the gold-conjugated, anti-CrAg antibodies. The gold-labeled antibody-antigen complex continues to wick up the membrane where it will interact with the test line, which has immobilized anti-CrAg monoclonal antibodies. The gold-labeled antibody-antigen complex forms a sandwich at the test line causing a visible line to form. Positive test results create two lines (test and control). Negative test results form only one line (control). If a control line fails to develop then the test is not valid.

- Blood specimens for CD4 counts will be sent to the participating laboratory performing the CD4 count, with a request to test for cryptococcal antigen in those samples with CD4  $\leq 100$  cells/ $\mu$ L. Remnant plasma from all specimens with CD4  $\leq 100$  cells/ $\mu$ L will be

